Contact information will be collected from participants, including cell phone and home phone numbers, home and work address, email address, and Facebook/social networking account information. We will also assess whether participants are willing to receive text reminders on their cell phone. Additionally, a reminder letter and a small gift (tote bag, etc) will be sent to every participant who is willing to receive mail 4 months after enrollment. These strategies have been shown to be effective in retaining participants in community-based research.

Data will be collected by study staff via surveys at baseline, 2, and 6 months. Scheduled office visits will be tracked via quarterly data pulls from the EHR system. If no visit is scheduled during the follow-up period, project CHWs will conduct follow-up calls to schedule participants for data collection events in the community, at the clinic, or at their home, with permission. Participants will be compensated \$25 for each assessments and will receive reminder calls and/or texts 2 weeks prior to data collection events to ensure attendance.

Substudy Biosample Collection. Substudy participants will have the option of mail or in-person pick-up for receiving study materials, which include the kits to collect oral wash and/or fecal samples and return stamped envelope. Once the substudy materials are received, study staff will set up an appointment to call or meet with substudy subjects remotely via WebEx and answer any questions about sample collection and return.

Substudy subjects will have the option to provide oral wash sample only, fecal sample only, or both. Study staff who have obtained the verbal consent will document the consent on the Enrolled Participants Log. The Enrolled Participants Log is the only record linking a participant's name, subject ID and substudy ID (if applicable).

Fecal biosample collection: Substudy participants will provide fecal samples (about 8 grams which is about 2 teaspoons) in a OMNIgeneGUT fecal sample tube (*DNAgenotek, Ontario, Canada*).

Directions for performing the test:

- 1) Remove the fecal sample tube with preservation liquid inside from packaging.
- 2) Flush the toilet, allow it to refill. The stool cannot touch the toilet bowl or water. Use one of the following collection options:
 - a. Place saran wrap or provided stool collection paper over the toilet bowl to collect a sample of stool.

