 - b. Just before finishing a bowel movement, use a piece of toilet paper to collect a small sample of stool.
- 3) Use spoon attached to cap to collect 2 marble sized samples.
- 4) Carefully screw the cap closed with sample on spoon. Shake well.
- 5) Once the collection is complete, place the tube in the preaddressed package and seal carefully. Return to the study center by mail within one day of collection.

Oral wash biosample collection: Study participants will be asked to swish vigorously with one aliquot of 10 ml Scope Original mouthwash sample (*Proctor & Gamble, Cincinnati, OH*) for 30 seconds.

Participants will be directed to expectorate the mouthwash into a clean specimen tube, and return to the study center by mail within one day of collection.

B. Data Analysis and Data Monitoring

B1. EHR-CHW Intervention Analysis.

We will conduct analyses to determine the comparability of the participants in the 2-arms using standard techniques, including Student's t-tests for normally distributed variables (after necessary transformations) and chi-squared tests for dichotomous variables. If the randomized groups differ in baseline characteristics, we will adjust for those variables in subsequent analyses of program effects. Descriptive statistics will be calculated to characterize study participants and to evaluate the distribution of key clinical, sociodemographic, and outcome variables. Summary data on medical history, years in the US, access to and utilization of primary health care services, and social characteristics (e.g., marital status, employment) will be reported.

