All analyses will be conducted using intention-to-treat methods to minimize the risk of attrition bias. The *primary analyses* of differences in *H. pylori* eradication between the intervention and usual care groups will first be tested using a chi-squared test of binomial proportions. We will assess level of participation for those randomized into the intervention arm, and explore whether level of participation is associated with greater changes in health outcomes. Logistic regression analysis will be used to analyze differences in outcome between those who receive the intervention and those who do not, controlling for potential confounding factors. All quantitative data will be entered and analyzed using standard statistical packages (e.g., SAS, R, Stata). The primary analysis will assume that any patient lost to follow-up failed to achieve *H. pylori* eradication. As a sensitivity analysis, we will apply multiple imputation to impute missing outcomes assuming a missing-at-random mechanism.

The analysis of *secondary outcomes* is guided in part by the Social Cognitive Theory. We hypothesize that the intervention group, when compared with usual care, will report: 1) increased medication adherence; 2) increased self-efficacy for adherence; 3) improved health literacy; 4) improved knowledge about stomach cancer prevention; and 5) higher levels of perceived health related quality of life. We will compare these intermediate outcomes between groups using t-test or its non-parametric equivalent, the Wilcoxon rank-sum test. Sex as a biological variable will be addressed by exploring gender as a potential moderator of intervention effects.

Power calculations. For the control group, we conservatively estimate that approximately 55% will achieve *H. pylori* eradication based on several studies of overall and, specifically, Chinese American populations.^{36,45,46,100} We wish to detect an increase in this rate to approximately 80% in the intervention group; this difference is reasonable based on studies in Ireland and China that showed increases of approximately this magnitude in rates of knowledge and high adherence in similar populations.^{36,44,45} Accrual of 144 participants, evenly randomized to intervention or usual care, provide greater than 80% power to detect this difference, using a 2-sided, 0.05-level test.

B1a. Substudy Data Analysis.

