There are no costs to participate in this study. Any doctor visits and laboratory tests, including the fecal antigen test or other clinically approved *H. pylori* infection diagnostic test, are part of standard care.

I. Payment for Participation

Participants will receive a payment of \$25 each time they complete a questionnaire (baseline, 2 months and 6 months). Participants may receive metro cards for travel associated with the project.

Substudy. Subjects will be given a \$20 gift card if they provide one type of sample only (either oral wash or stool), and a \$35 gift card if they provide both oral wash and stool samples. Gift cards will be mailed or given to subjects upon successful return of biosamples collected post-*H. pylori* medication completion.

J. Subject Withdrawal

Any of the participants may withdraw from the study at any time. This will not affect their services and care at the clinic site. If a participant is uncomfortable during an interview or survey administration, the participant may stop at any time without penalty. If a participant withdraws consent, no further data from that participant will be collected.

Early Termination. The study may be suspended or prematurely terminated if there is sufficient reasonable cause. Written notification, documenting the reason for study suspension or termination, will be provided by the suspending or terminating party to the investigator and/or the NIH NIMHD, as applicable. If the study is prematurely terminated or suspended, the PI will promptly inform the Institutional Review Boards (IRBs) and provide the reason(s) for the termination or suspension. Circumstances that may warrant termination include, but are not limited to:

- Determination of an unexpected, significant, or unacceptable risk to subjects.
- Insufficient adherence to protocol requirements.
- Data that are not sufficiently complete and/or evaluable.

VII. FUNDING SOURCE

The main study is supported by NIH-NIMHD U54 MD000538. The substudy is supported by NIH-1P20CA252728-01

VIII. APPENDIX

- A. Combined Script for Telephone Screening
- B. Screening Form for CHW Intervention
- C. Combined Verbal Informed Consent
- D. Key Information Sheet for CHW Intervention
- E. Key Information Sheet for Substudy
- F. Baseline Survey for CHW Intervention
- G. Follow-up Survey for CHW Intervention
- H. Script for Substudy Telephone Text Reminders
- I. Substudy Instruction Booklet
- J. Key Informant Interview Guide

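### Secondary scales: pre-specified adjustment for a pre-randomization baseline score would be at least as precise as the planned t-test, at very little cost (optional improvement)

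*Combined protocol and SAP*

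**What the plan says.** Section III.B1 lists five hypotheses on secondary outcomes: adherence, self-efficacy, health literacy, knowledge and health-related quality of life. The analysis is one sentence: "We will compare these intermediate outcomes between groups using t-test or its non-parametric equivalent, the Wilcoxon rank-sum test". No covariate is named.

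Baseline adjustment appears earlier in III.B1. The arms are first compared: "We will conduct analyses to determine the comparability of the participants in the 2-arms using standard techniques", namely t-tests and chi-squared tests, with no significance threshold. Then: "If the randomized groups differ in baseline characteristics, we will adjust for those variables in subsequent analyses of program effects".

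The baseline information is already being gathered. Section III.A2 states: "Data will be collected by study staff via surveys at baseline, 2, and 6 months". Section C2 gives the same schedule, section VI.I pays participants for each of the three questionnaires, and Appendix F is listed as "Baseline Survey for CHW Intervention". Its items are not shown.

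No section pre-specifies ANCOVA, a repeated-measures model or any other routine adjustment for a scale's own baseline score. The only regression named is logistic, for outcome differences, with unnamed confounders.

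**The concern.** When a scale is measured before and after randomization, its baseline score usually predicts its follow-up score. A two-sample t-test or Wilcoxon test on follow-up scores leaves that information unused. A test on change scores uses it with a fixed weight of one, which is too much when the correlation is modest.

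The III.B1 rule does not repair this. It depends on the observed data, has no threshold, and needs a model that neither named test supplies. Adjusting only after an observed imbalance also forgoes most of the benefit, because adjustment raises precision even when the arms are balanced.

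What is at stake is power for the secondary hypotheses. The plan's only power statement concerns eradication, so power for these scales is unstated. Validity is not at stake, nor is the primary analysis.

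**Working it through.** **1. The plan's own figure.** From III.B1: 72 per arm, 55% against 80% eradication, two-sided 0.05. The mean proportion is 0.675. Power = Φ[(0.25·√72 − 1.96·√(2·0.675·0.325)) / √(0.55·0.45 + 0.80·0.20)] = Φ[(2.121 − 1.298)/0.638] = Φ(1.289) = 90.1%. The stated value of more than 80% holds, but it says nothing about the scales.

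**2. Inputs for the scales.** The documents give 144 participants, 1:1 allocation, and surveys at baseline, 2 and 6 months. The two-sided 0.05 level is stated for eradication and assumed here. The correlation r, the effect size, the loss rate and the adjustment trigger are not given; all are assumptions, shown over ranges. Scores are in SD units.

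**3. Variance factors** (multiplying 2/n for the difference between arms):

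- follow-up score: 1
- change score: 2(1 − r)
- ANCOVA: 1 − r²

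Since 1 − r² ≤ 1, and 2(1 − r) − (1 − r²) = (1 − r)² ≥ 0, ANCOVA is at least as precise as either t-test, apart from one degree of freedom.

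| r | Follow-up | Change | ANCOVA | ANCOVA / better t-test | Equivalent n per arm |
|---|---|---|---|---|---|
| 0.3 | 1 | 1.40 | 0.91 | 0.91 | 72/0.91 = 79 |
| 0.5 | 1 | 1.00 | 0.75 | 0.75 | 72/0.75 = 96 |
| 0.7 | 1 | 0.60 | 0.51 | 0.85 | 72/0.85 = 85 |

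**4. Power, 72 per arm, 0.4 SD.** The noncentrality is 0.4/√(2/72) = 2.40, divided by the square root of the factor. Power is from the noncentral t distribution (142 df, or 141 for ANCOVA, averaged over chance baseline imbalance).

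| r | Follow-up t | Change t | ANCOVA | Gain over better t-test |
|---|---|---|---|---|
| 0.3 | 66.4% | 52.2% | 70.2% | 4 points |
| 0.5 | 66.4% | 66.4% | 78.3% | 12 points |
| 0.7 | 66.4% | 86.8% | 91.4% | 5 points |

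At r = 0.2 the gain is only 1 to 2 points. At r = 0, ANCOVA gives 66.1%, a loss of about 0.3 points. For r = 0.3/0.5/0.7 the gain is 3/11/7 points at 0.3 SD and 3/8/2 at 0.5 SD. At 0.4 SD with 61 per arm (15% loss) it is 4/12/6.

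**5. The conditional rule.** This assumes that the rule covers the scale's own baseline score, which is not stated, and falls back on the follow-up t-test. Simulation: 100,000 trials per setting, 72 per arm, r = 0.3/0.5/0.7.

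| Trigger | Power at 0.4 SD | Type I error |
|---|---|---|
| p < 0.05 | 67/67/68% | 4.7/4.2/3.7% |
| p < 0.20 | 68/70/73% | 4.5/3.7/2.7% |
| p < 0.50 | 69/73/81% | 4.5/3.8/3.0% |
| ANCOVA always | 70/78/91% | 4.9/4.9/5.1% |

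The rule recovers only part of the gain and is conservative. When the trigger does not fire, the imbalance is smaller than chance would give, so the unadjusted standard error is too large. With a change-score fallback, power is also below routine ANCOVA at each trigger tried.

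**6. Non-normal scores.** On a bounded 11-level scale with about 20% at the ceiling (20,000 trials), t-test and Wilcoxon each give 62%, and ANCOVA gives 65/73/86%. On strongly skewed scores (4,000 trials, 0.4 SD shift) the order changes:

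| r | Wilcoxon | Linear ANCOVA | Rank-based ANCOVA |
|---|---|---|---|
| 0.3 | 63% | 50% | 67% |
| 0.5 | 65% | 55% | 77% |

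**The case against.** A reader might infer that adjustment beats both tests the plan names. It does not. The result in step 3 covers t-tests on follow-up or change scores. The plan names Wilcoxon as the alternative, and linear ANCOVA has no such guarantee against it; step 6 shows losses of 13 and 10 points on strongly skewed scores. The score distributions are not given. This objection stands, and it is why skewed scales need the rank-based version, which led Wilcoxon in the skewed settings tried.

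The low cost also depends on the baseline score being taken before randomization. The documents say only that surveys occur at baseline and that consented participants are randomized; they do not state the order. As an illustration, suppose the intervention had already shifted the baseline survey by 0.2 SD, with a true effect of 0.4 SD and r = 0.5. The adjusted estimate would be 0.4 − 0.5·0.2 = 0.30 SD, with power of 54% against 67% unadjusted. Baseline normally means before randomization, so this is a condition to write down. It is not a demonstrated fault.

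The size of the gain rests wholly on assumed values, and r = 0.5 is where the precision gain over the better t-test peaks. That stands, and is why the range is shown.

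It is fair to say that the III.B1 rule implies some model, even though none is named. Whether its baseline characteristics include scale scores is unknown, so step 5 is conditional on that reading.

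A reader might also infer that the planned tests are biased or that the conditional rule inflates false positives. Neither is supported: randomization makes the unadjusted tests valid, and the rule errs on the conservative side.

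The plan does not say which visit, or whether follow-up or change scores, will be compared. The phrase "explore whether level of participation is associated with greater changes in health outcomes" concerns participation within the intervention arm and does not settle it. This is a separate gap in detail, and the present point does not rest on it.

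**Conclusion.** The point holds as an optional improvement in efficiency, for secondary scales with a meaningful baseline score taken before randomization. Medication adherence is excluded because a course of treatment not yet begun has no meaningful baseline. For roughly normal scores at 72 per arm and 0.4 SD, the gain over the better t-test is 4, 12 and 5 points of power at r = 0.3, 0.5 and 0.7. It is small at r = 0.2 and slightly negative at zero. These figures depend on assumed correlations and effect sizes. For clearly skewed scales the case rests on the rank-based form, not on linear ANCOVA.

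The planned tests remain valid, the eradication analysis and its power are untouched, and no wrong conclusion has been shown.

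**What to change.** For each scale in the baseline survey that is completed before randomization:

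- Pre-specify as the main analysis ANCOVA with arm and baseline score, or a baseline-adjusted repeated-measures model over 2 and 6 months.
- For clearly skewed scales, pre-specify ANCOVA on the ranks of the follow-up and baseline scores in place of Wilcoxon.
- Let this replace the test-then-adjust rule of III.B1 for these scales.
- Keep the t-test or Wilcoxon test as a robustness check, and as the analysis for adherence.
- Do not adjust for a survey completed after randomization or after session 1.

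The cost is SAP wording, one degree of freedom and a rule for missing baseline scores; no new data are needed. The analysis also rests on a missing-at-random type assumption. That applies to single-visit complete-case ANCOVA as well as to the repeated-measures model, and should be stated. III.B1 currently makes it only in a sensitivity analysis: "As a sensitivity analysis, we will apply multiple imputation to impute missing outcomes assuming a missing-at-random mechanism".

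### The main comparison of the five secondary survey scales uses only participants with a score at the visit tested, so the plan's aim of limiting attrition bias is not carried into these analyses

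*Combined protocol and SAP*

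**What the plan says.** Section III.B1 (EHR-CHW Intervention Analysis) opens its analysis plan with a general commitment: "All analyses will be conducted using intention-to-treat methods to minimize the risk of attrition bias". Two missing-data rules follow in the same paragraph, which deals with eradication. The main one is "The primary analysis will assume that any patient lost to follow-up failed to achieve *H. pylori* eradication". The other is "As a sensitivity analysis, we will apply multiple imputation to impute missing outcomes assuming a missing-at-random mechanism".

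The next paragraph lists five secondary hypotheses: medication adherence, self-efficacy, health literacy, knowledge and health-related quality of life. Their analysis is one sentence: "We will compare these intermediate outcomes between groups using t-test or its non-parametric equivalent, the Wilcoxon rank-sum test". It names no visit, no covariate and no handling of missing scores.

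Section III.A2 (Data Collection) gives the survey schedule: "Data will be collected by study staff via surveys at baseline, 2, and 6 months". Section III.B1 also has a conditional adjustment clause: "If the randomized groups differ in baseline characteristics, we will adjust for those variables in subsequent analyses of program effects".

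**The concern.** A t-test or rank-sum test can use only observed scores. Someone who completes the baseline and month-2 surveys but misses month 6 drops out of a month-6 comparison, and their month-2 score is not used. Counting a missing result as a failure suits a yes/no outcome but has no meaning for a scale. Multiple imputation, even if read to cover the scales, would leave the main comparison as complete-case. The adjustment clause brings back no one without a follow-up score.

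At stake are the estimates for all five secondary hypotheses. If the reason for missing a survey differs by arm and is related to the score, the difference between completers is not the difference between the randomised groups. If it does not differ, the loss is mainly of precision.

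**Working it through.** **The plan's own figure.** The only power statement concerns eradication, 55% against 80%, with 72 per arm and two-sided 0.05:

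z = [0.25√72 − 1.96√(2 × 0.675 × 0.325)] / √(0.55 × 0.45 + 0.80 × 0.20) = (2.121 − 1.298) / 0.638 = 1.29, so power is 90.1%.

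The stated figure of more than 80% is right. No power is given for the secondary scales.

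**Inputs.** From the documents: 144 participants, 1:1, hence 72 per arm; surveys at baseline, 2 and 6 months; two-sided 0.05, carried over from the primary test. Assumed, because the documents give no survey attrition, SD or correlation: correlation 0.6 between visits, true difference 0.5 SD, and 10 to 30% missing follow-up scores.

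**Step 1: precision only, scores missing at random.** Power = Φ(0.5√(n/2) − 1.96); difference detectable with 80% power = (1.96 + 0.842)√(2/n).

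| Missing | Total analysed | Detectable difference (SD) | Power for 0.5 SD |
|---|---|---|---|
| 0% | 144 | 0.47 | 85% |
| 10% | 130 | 0.49 | 81% |
| 20% | 115 | 0.52 | 77% |
| 30% | 101 | 0.56 | 71% |

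Here the t-test is unbiased.

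**Step 2: when the t-test is biased.** Let m be the fraction missing in an arm and g the amount by which the observed mean exceeds the mean of the missing. The completer mean is then too high by m × g, and the arm difference is off by m(CHW) × g(CHW) − m(control) × g(control). This vanishes when the two products are equal.

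**Step 3: dropout tied to a low month-2 score (logit slope 1 per SD) in controls only, random in the CHW arm.** The likelihood estimate is b + c × a. Here b and c are the arm and month-2 coefficients from regressing month 6 on arm, baseline and month 2 among completers. The term a is the arm coefficient from regressing month 2 on arm and baseline in everyone. Simulated results, which move slightly between runs:

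| Analysis | Missing | Estimate (true 0.50 SD) | Power | Type I error, no effect |
|---|---|---|---|---|
| Completer t-test | 20% | 0.39 | 56% | about 9% |
| Likelihood, baseline and month 2 | 20% | 0.50 | 91% | about 5% |
| Completer t-test | 30% | 0.35 | 41% | 11 to 13% |
| Likelihood, baseline and month 2 | 30% | 0.50 | 87% | about 5% |

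At 20% the bias is 0.39 − 0.50 = −0.11 SD, against the intervention. By Step 2 this corresponds to −0.20 × g with g = 0.55 SD.

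**Step 4: how much belongs to baseline adjustment.** At 20% missing, complete-case ANCOVA on baseline gives 0.46 SD, about 85% power and about 6% type I error. It recovers (0.46 − 0.39)/(0.50 − 0.39) = 64% of the bias and 85 − 56 = 29 of the 91 − 56 = 35 points of power. A likelihood analysis with month 2 but no baseline gives 0.50 SD, with 78% power at 20% missing and 73% at 30%. So month 2 removes the bias in this scenario, while most of the power comes from baseline.

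**Step 5: other mechanisms.**
- Same month-2 mechanism in both arms: the t-test estimates 0.47 SD (20% missing) and 0.46 SD (30%), with type I error of 4.6% and 5.1%.
- Low-baseline participants dropping out more in the CHW arm only (dropout at the mean baseline 10% control, 20 or 30% CHW), no true effect: the t-test shows a false benefit of 0.12 to 0.16 SD with type I error of 10 to 13.5%. Baseline adjustment gives bias near 0 and about 5%.
- Control dropout driven by the month-6 score itself, 20% missing: the likelihood analysis also fails, with 10.6% false positives.

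**The case against.** The strongest reply is that nothing in the documents shows differential loss. The retention measures in Section III.A2 are not limited by arm: the letter and gift at 4 months, payment per assessment, reminders before data collection, and calls with flexible locations for those without a scheduled visit. A reader might infer that controls have no continuing contact; the documents do not support that. What the CHW arm has in addition is the four sessions and the medication and follow-up reminders (Section III.A1). That makes different response possible, not established.

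A reader might also infer that the plan breaks its intention-to-treat commitment. It does not: people are still compared by randomised arm. What falls short is the stated purpose of limiting attrition bias. The imputation sentence could be read to include the scales, but that would add only a sensitivity analysis.

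Three further replies stand in part. The size in Step 3 depends on one-sided dropout, and there the bias understates benefit. Baseline adjustment alone would deliver most of the power. A baseline, 2- and 6-month model may not suit every scale: adherence concerns a 14-day course (Section B5), the registry route looks for patients diagnosed within 7 days, and the documents show no pre-treatment adherence score.

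None of this makes a completer t-test the better main analysis when a second follow-up survey is already collected.

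**Conclusion.** The point holds as a choice of method. The main secondary comparison is complete-case, and neither missing-data rule changes that. Under the assumptions above, dropout tied to a low month-2 score in controls only costs about 0.11 to 0.15 SD (0.50 − 0.39; 0.50 − 0.35) of a 0.5 SD effect and raises type I error to about 9 to 13%. Baseline-related dropout in the CHW arm would push the other way. With random or like-for-like dropout there is little or no bias, and the main loss is of precision.

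Two stronger conclusions are not supported. One is that the secondary results will be biased: no attrition rate or pattern is given. The other is that the rise from 56% to 91% power comes from handling missing data: 29 of those 35 points come with baseline adjustment alone. The eradication analysis has its own rule and is not affected. The change should be made because it is cheap and serves the plan's own aim.

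**What to change.** In Section III.B1, make the main analysis of each secondary scale a mixed model for repeated measures with arm, visit and arm-by-visit.

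- Use every survey available for that scale: baseline, 2 and 6 months where a baseline score exists, and only the two follow-up visits where no pre-treatment score exists, as may be so for adherence.
- Where baseline is a response, give both arms a common baseline mean, as randomisation justifies. The follow-up contrasts then gain from baseline, and participants with only a baseline score stay in.
- Include every randomised participant with at least one score, and report the arm contrast at each follow-up visit.
- Keep the t-test or Wilcoxon as a supportive complete-case analysis.

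The cost is wording and a standard model, with no new data or participants. The model relies on scores being missing at random, which the plan already assumes in its eradication sensitivity analysis. It does not protect against dropout that depends on the unseen score, so a brief sensitivity analysis for that case is worth adding.
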